**Secondary:**

1. To determine the kinetics of SARS-CoV-2 antibodies and cellular immune response in early, mid, and long periods of immunization.
2. To assess the relation between clinical variables and initial RT-PCR results with the interindividual differences in the immune response in early, mid, and long periods of immunization.
3. To analyze differentially expressed cytokines as biomarkers of disease progression in early, mid, and long periods of immunization.

**Methods and analysis:** Longitudinal, dynamic, prospective cohort study with a 12-month follow-up, which is being conducted in 4 primary-care centres and one hospital of Northern Metropolitana Nord of Barcelona (Spain). For now, the study consists of 1350 participants divided into 2 cohorts: 1) Healthy-Exposed HCWs: 675 not infected by SARS-CoV-2 (RT-PCR with a negative result and negative SARS-CoV-2 antibodies at baseline) and 2) Infected HCWs: 675 symptomatic participants (those with new persistent cough, temperature  $\geq 37.5^{\circ}\text{C}$ , anosmia, or ageusia or other compatible symptoms with COVID-19) or asymptomatic participants diagnosed by positive RT-PCR test and/or SARS-CoV-2 antibodies (IgM, IgG at baseline). Primary outcomes include: humoral and cellular immune response, quantitative antibodies to SARS-CoV-2, SARS-CoV-2 antibody levels related to progression phenotype, clinical spectrum of SARS-CoV-2, symptomatology, demographics and other variables that may be predictive of immune response.

**Follow-up:** baseline, 15 days, 1, 3, 6, 9 and 12 months.

**Findings to date:** Current literature has shown that the immune response is maintained for a minimum of 2 months. Nevertheless little is known about the association between the immune response and the progression phenotype of COVID-19.

**Future plans:** This prospective cohort offers the possibility to study associations between immune response and progression phenotype according to age and gender as well as long-term immune response. In turn, we will be able to examine possible cumulative effects, taking into account several

clinical variables. The study is ongoing and we plan to extend it to increase the size of the cohort until 2024.

**Ethics and dissemination:** The study is approved by the Ethics Committee (IDIAPJGol ref 20/067-PCV IGTP ref COV20/00660 (PI-20-205). Dissemination will occur through presentations at National and International conferences and publications in international peer-reviewed journals.

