#### 6.5. PROCEDURES

Participants entering the study after meeting exclusion/exclusion criteria (Table 1), give written informed consent (informed consent and patient information sheet, see Appendix 1) and they are assigned to a cohort (Figure 1). Cohorts are divided into:

- 1) Healthy pre-cohort: HCW exposed to but not infected with SARS-CoV-2, negative PCR-test or Ig M (N) and IgG (N)
- 2) Non-recent Infected cohort: HCW infected with SARS-CoV-2 (>15 days RT-PCR, positive)
- 3) Recent Infected cohort infected HCW : HCW with acute SARS-CoV-2 infection (<15 days RT-PCR, positive)

All participants undergo a standardised follow-up according to the specific cohort to which they are assigned (Table 2). At study entry, we record the following information: baseline socio-demographic

data, clinical data (symptoms), epidemiological data (contact with a positive and symptoms of COVID-19) (table 3), information on the work environment, data on the diagnosis of COVID-19 (previous biological samples taken and dates of sick leave due to COVID-19), use of personal protective equipment, previous health status and habits. At subsequent visits, epidemiological data, clinical data (symptoms) and vaccinations are recorded.

Finally, initial participant's cohort assignation is reviewed and reclassified on basis on laboratory results (RT-PCR test or SARS-CoV-2 antibodies IgM and IgG against the nucleocapsid (N)) in two final cohorts:

1) Health Care Workers Healthy Cohort (HCW\_H): This cohort includes HCW with negative laboratory test RT-PCR and SARS-CoV-2 antibodies IgM(N), and IgG(N).

2) Health Care Workers Infected Cohort (HCW\_I): This cohort includes HCW with positive laboratory test (RT-PCR and/or SARS-CoV-2 antibodies IgM and IgG) This cohort is subdivided into three categories according to the illness severity:

Asymptomatic or Presymptomatic Infection: Individuals with positive laboratory evidence of COVID-19 but no COVID-19 signs nor symptoms.

Mild-Moderate Illness: Individuals with positive laboratory evidence of COVID-19 who have any of the various signs and symptoms of COVID-19 (e.g., fever, cough, sore throat, malaise, headache, muscle pain, nausea, vomiting, diarrhea, loss of taste and smell) but who do not have shortness of breath, dyspnea, or abnormal chest imaging and home health care.

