A) RT-PCR will be used as diagnostic test every 2 weeks RNA for RT-PCR tests will be extracted from fresh samples using the STARMag 2019-nCoV kit (Seegene, CA, USA) on a liquid-dispensing robot (STARlet Hamilton, USA). To inactivate the virus and extract viral RNA, 500 µl of the transfer medium containing the swab is combined with 500 µl of lysis buffer of the STARMag kit in a BSL-2 laboratory; following 10' of incubation at room temperature, 350 µl was used for nucleic acid extraction into a volume of 100 µl of extracted genome, from which 8 µl was taken for the 2019-nCoV PCR assay. The detection of RNA will be performed using the Allplex™ SARS-CoV-2 Assay is a multiplex real-time PCR

assay to detect 4 target genes of SARS-CoV-2 in a single tube. The assay is designed to detect RdRP, S and N genes specific for SARS-CoV-2, and E gene for all of Sarbecovirus including SARS-CoV-2 (Seegene, CA, USA) according to the manufacturer's instructions.

B) Quantification of antibodies to SARS-CoV-2. We performed a previous validations study with 6 different IVD-CE approved ELISA tests and selected the commercially available test kits - the AntiSARS-CoV-2 IgG and IgM ELISA (Inmunodiagnostic). This ELISA test had a Sensitivity 92.5% and a specificity 93.3% for IGM and IgG against Nucleocapsid (N) and Spike (S) antigens. For this, the best reagents and the most relevant antigen specificities will be analysed. We will perform test at baseline, 7 days, 15 days, 3, 6, 9 and 12,16,20,24 months after the beginning of the study.

We conducted a pre-validation study (March-April 2020) with 6 different IVD-CE approved ELISA tests and selected commercially available Anti-SARS-CoV-2 IgG and IgM ELISA kits (Inmunodiagnostic Limited ©). These ELISA tests had a sensitivity of 92.5% and a specificity of 93.3% for IGM and IgG against the nucleocapsid (N) antigen. Positivity thresholds were provided by the assay manufacturers and were considered positive with an index value greater than 1.1, indeterminate from 0.9 to 1.1 and negative if <0.9 index units.

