Positive participants with Rt-PCR + or IgM (N) or IgG (N) were also tested for antibodies against the Spike (S) subunit of SARS-CoV-2. This was done by enzyme immunoassay for the qualitative determination of IgG class antibodies against COVID-19 (SARS-CoV-2) in human serum with DECOV1901. This reagent complies with the technical specifications for sensitivity, specificity, and standardisation according to WHO International Standards and Reference Panel for anti-SARS-CoV-2 antibody (WHO/BS.2020.2403). Positivity thresholds were provided by the assay manufacturers and were considered positive with an index value greater than 40, indeterminate from 32 to 40 and negative if <32 UI/ml

Positive participants for serology or/and RT-PCR were also tested for antibodies against the Spike (S) subunit of SARS-CoV-2. This was done by enzyme immunoassay for the quantitative determination of IgG class antibodies using DECOV1901 (Demeditec Diagnostics GmbH©). This reagent complies with the technical specifications for sensitivity, specificity, and standardisation according to WHO International Standards and Reference Panel for anti-SARS-CoV-2 antibody (WHO/BS.2020.2403). Positivity thresholds were provided by the assay manufacturers and were considered positive with an index value greater than 40, indeterminate from 32 to 40 and negative if <32 UI/ml

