##### NONLINEAR MIXED-EFFECTS (NLME) MODELS

Mixed-effects models are generally useful when there are multiple measures per participant, as in this study. Random effects are included in the model to test if they may be causing any significant, and generally unexpected, significant influence in the modelling built by the fixed effects. Therefore, introducing random effects in the model help to control unobserved variance.

We will use NLME models to study possible differences in the dynamics (kinetics) of SARS-CoV-2 antibodies (IgM, IgG) levels since symptoms onset. After fitting a general model, the differences will be studied between clinical spectrums and biological sex, setting the largest group as reference groups for modelling. To fit these models, we will use all the data available except for those from participants who never tested positive. Time after diagnosis was discretized as follows: Tests made in the first 14 days since diagnosis are treated as "Day 15". Tests from days 15 to 29, as "Day 30", days 30 to 59 as "Day 60", days 60 to 89 as "Day 90", days 90 to 179 as "Day 180", days 180 to 269 as "Day 270", days 270 to 360 as "Day 360", and days 360 up to end of follow-up as "Day 450". However, antibody values beyond 450 days after diagnosis were not considered, as they were only available for 14 participants.

The general equations to be fitted will be:

$$IgM(t) = b_1 + (b_0 - b_1)e^{-k_1 t} - b_1 k_1 (e^{-k_1 t} - e^{-k_2 t})$$

$$IgG(t) = b_1 + (b_0 - b_1)e^{-k_1 t} - b_1 k_1 (e^{-k_1 t} - e^{-k_2 t})$$

Having  $t$  normalized per the maximum number of days (360). This general equation corresponds to an equation describing an exponential rise followed by an exponential decay.  $b_0$  corresponds to the baseline value,  $b_1$  corresponds to the asymptotic value (i.e., antibody levels at  $t \rightarrow \infty$ ),  $k_1$  corresponds to the rise rate, and  $k_2$  to the decay rate.

Nonlinear mixed-effects models will be built using the nlme package [14].

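### One unconfirmed positive on an N ELISA with 93.3% specificity admits a worker to the kinetic curves and can label them infected, and no confirmed-case analysis is planned

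*Combined protocol and SAP*

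**What the plan says.** **Assay.** Section 6.6, item 16 B, states that "These ELISA tests had a sensitivity of 92.5% and a specificity of 93.3" per cent for IgM and IgG against N. An adjoining paragraph gives the same two figures "for IGM and IgG against Nucleocapsid (N) and Spike (S) antigens". Neither says whether they apply to each isotype or to the pair, and no validation counts are given. A result is "considered positive with an index value greater than 1.1, indeterminate from 0.9 to 1.1 and negative if <0.9 index units". No repeat or second assay is required.

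**Cohort label.** Section 6.5 defines the final infected cohort thus: "This cohort includes HCW with positive laboratory test (RT-PCR and/or SARS-CoV-2 antibodies IgM and IgG". The healthy cohort must be negative on RT-PCR, IgM (N) and IgG (N). The same section says the initial assignment is revised on laboratory results, but not when. The abstract has infected workers "diagnosed by positive RT-PCR test and/or SARS-CoV-2 antibodies (IgM, IgG at baseline". Table 5 still lists workers who had antibodies at Visit 4 in Healthy HCW rows.

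**Either or both isotypes.** Section 6.6, item 8 and the first Spike paragraph of item 16 B join IgM (N) and IgG (N) with an or. Section 6.5 joins them with an and.

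**Kinetic set.** For the NLME models, "we will use all the data available except for those from participants who never tested positive". The LOESS paragraph has the same exclusion.

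**Asymptomatic class.** Section 6.5: "Individuals with positive laboratory evidence of COVID-19 but no COVID-19 signs nor symptoms".

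**Spike.** "Positive participants for serology or/and RT-PCR were also tested for antibodies against the Spike (S) subunit of SARS-CoV-2". The result is a secondary outcome (6.6.2, item 6) and plays no part in the cohort rule.

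**The concern.** An ever-positive rule applied to a repeated test with imperfect specificity admits more false positives with each test, unless the errors are fully repeated within a person. No step in the plan removes them: a negative RT-PCR does not override a positive ELISA, and the second antibody result on positives is not consulted.

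Hypothesis 1 (Section 5.1) is that kinetics differ across clinical spectra. A falsely positive worker without symptoms meets the asymptomatic definition. False positives can therefore be more common in that class than in the severe one, and part of any difference between the curves could then reflect the test and not the disease. Incidence, which the primary aim stresses, would also be overstated where serology counts towards it.

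**Working it through.** **Inputs**
- Specificity 0.933, so a false-positive rate of 0.067 per test (Section 6.6). It cannot be reproduced, because no counts are given.
- 675 workers per cohort (Section 6.1), used here as a reference group of never-infected workers who attend every test.
- Number of tests k. Section 6.6.2 lists seven time points to month 12, and Section 6.5.1 lists ten to month 24. The healthy rows of Tables 2 and 5 show six or seven. The main figure uses k = 7.
- Within-person correlation of errors is not given. The range from 0 to 1 is shown.

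**1. 93.3% taken as the combined per-visit specificity**

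One test: 0.067 × 675 = 45.

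Independent errors, P(at least one) = 1 − 0.933^k:

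| k | Proportion | Of 675 |
|---|---|---|
| 1 | 6.7% | 45 |
| 6 | 34.0% | 230 |
| 7 | 38.5% | 260 |
| 10 | 50.0% | 338 |

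Correlated errors, k = 7, by a beta-binomial model with mean 0.067 and correlation ρ. With a = 0.067(1 − ρ)/ρ and b = 0.933(1 − ρ)/ρ, P(at least one) = 1 − ∏(b + j)/(a + b + j), j = 0 to 6. At ρ = 0.5, a = 0.067 and b = 0.933, so the product is 0.933/1 × 1.933/2 × … × 6.933/7 = 0.838.

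| ρ | Proportion | Of 675 |
|---|---|---|
| 0 | 38.5% | 260 |
| 0.2 | 26.0% | 175 |
| 0.5 | 16.2% | 110 |
| 0.8 | 10.0% | 67 |
| 1 | 6.7% | 45 |

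**2. 93.3% taken as per isotype, errors independent**
- Either isotype counts: per visit 1 − 0.933² = 13.0%; over seven, 1 − 0.933^14 = 62.1% (419 of 675).
- Both required: per visit 0.067² = 0.4% (3); over seven, 1 − (1 − 0.00449)^7 = 3.1% (21).

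The isotype rule and the meaning of 93.3% therefore move the seven-test figure from 3.1% to 62.1%.

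**3. What confirmation would leave (k = 7, independent errors, combined specificity)**
- Spike IgG also positive: 1 − (1 − 0.067(1 − s))^7, where s is the Spike specificity. The documents do not give s. For an assumed s of 90% the result is 4.6% (31 workers); for 99.5% it is 0.2% (2).
- N positive at two consecutive visits: 2.5% (17).
- If either route counts as confirmation, at most the sum remains: 31 + 17 = 48 down to 2 + 17 = 19.
- With fully repeated N errors, the two-visit route removes none of the 45. Only Spike could.

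**The case against.** **Effect of the isotype wording.** It is tempting to say that the problem is the same however that wording is resolved, and that 45 workers is a floor. Neither holds. If 93.3% is per isotype, errors are independent and both isotypes are required, about 3 of 675 are false at one test and 21 over seven.

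**Accumulation in the cohort label.** A reader might infer that a positive at any of seven visits makes a worker infected. The documents show accumulation only for the kinetic set. For the label they conflict: the abstract points to baseline, Section 6.5 gives no date, and Table 5 keeps antibody-positive workers in Healthy rows. If baseline alone decides, nothing accumulates there.

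**Size of the seven-visit figure.** Under the combined reading, 38.5% is an upper value for seven tests. It needs independent errors and full attendance, while the plan itself allows 10% dropout.

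**Share of the asymptomatic class.** A reader might want to state what share would be false. The documents give no true asymptomatic fraction, and the background calls the initial symptoms non-specific, so some false positives would be classed mild-moderate. With an assumed 10% to 40% of 675 truly asymptomatic, 45 to 260 false positives, and half or all of them landing in the class, the share runs from 8% to 79%. That is too wide to report as a finding.

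**Shape of the bias.** One might predict a spuriously weak, short-lived asymptomatic response. Nothing in the documents describes the index values or persistence of false positives, and repeated errors would not fade.

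**Confirmation as an entry rule.** N and Spike kinetics are outcomes 4 to 6. Requiring Spike positivity or repeat N for the main curves would select on the outcome and remove genuine weak or transient responders. This stands, and it is why the confirmed-only analysis should be secondary.

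None of this supplies the missing confirmation rule.

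**Conclusion.** The point holds in limited form. One unconfirmed N positive is enough to enter the LOESS and NLME sets and can place a worker in the infected cohort, while the Spike result on positives is not used to confirm.

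If 93.3% is the combined per-visit specificity, 6.7% of never-infected workers are false positives at one test. Over seven tests the figure lies between 6.7% and 38.5%, depending on within-person correlation. On the per-isotype reading with independent errors, it is 3.1% or 62.1% according to the isotype rule.

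Accumulation is clear for the kinetic set and unresolved for the cohort label. Bias in the clinical-spectrum comparison is possible, but its size and direction cannot be fixed from the documents. The plan should be changed, though nothing here shows that the planned comparison is invalid.

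**What to change.** **Section 6.5**
- State one isotype rule, consistent with Section 6.6, and say when reclassification takes place. Bring the abstract and Table 5 into line.
- Define confirmed infection as any of: positive RT-PCR; N positive with Spike IgG above 40 (the plan's own threshold) in a sample taken before vaccination; or N positive at two consecutive visits. The vaccination limit is needed because vaccination is recorded during follow-up and the plan has no rule for reading Spike IgG afterwards.
- Hold other N positives in a separate unconfirmed category. They do not fit the healthy cohort, which is defined as N negative.

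**Section 6.6.** Report the validation counts and the specificity by isotype and for the pair, and give the Spike specificity.

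**Sections 6.8.2.1 and 6.8.2.2.** Keep the ever-positive set. Add a pre-specified repeat of the kinetic curves and clinical-spectrum comparisons in confirmed cases only. Report both, and call a spectrum difference robust only if it appears in both.

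**Cost.** Mostly wording, since Spike on positives and later N tests are largely planned already. Two things need checking: Section 6.6 does not say that Spike is run on the same sample as the positive N result, and Tables 2 and 5 do not schedule it by visit. The confirmed-only set loses some true infections with weak or transient responses, cannot use the repeat-N route for a first positive at the last visit, and still contains some false positives. It should therefore remain a sensitivity analysis.

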### C) Additional Immune response laboratory assays:

C1) Additionally, blood samples of HCW (infected and healthy participants) will be collected and stored for more exhaustive determinations of the immune response in later studies.

C2) INF $\gamma$  Elispot assays. To monitor both SARS-CoV-2 specific CD4+ and CD8+ T-cell responses we performed an INF $\gamma$  ELISPOT assay. The design compromises a comprehensive screening using peptide pools for the nucleocapsid, membrane, S1 and S2 regions of the spike protein described in Olvera et al., (2020) vaccines and total recombinant proteins for the nucleocapside and the spike. In brief, cells will be thawed and incubated overnight at 37°C in the presence of SARS-CoV2 peptide pools described (5ug/ml for each peptide) and PHA (15  $\mu$ g/ml), as positive control. Finally, plates were revealed with biotinylated anti-human INF $\gamma$ , streptavidin-alkaline phosphatase and its coloured substrate (Mabtech, Sweden).

IFNy secreting cells were quantified under Immuno Capture and Immuno Spot software to calculate the number of Spot Forming Cells (SFC). Cryopreserved PBMCs will be stimulated overnight with CoV-2 peptide pools (5ug/ml for each peptide) and PHA (15 µg/ml), as the positive control. Spot Forming Cells (SFC) will be counted using an INFg-ELISpot kit (Mabtech), AP-conjugate kit (BioRad) and an automated ELISPOT Reader Unit (CTL) as previously described (Dalmau et al AIDS 2014). Wells will be considered positive if they contained at least 50 spot-forming cells per 10^6 PBMCs above the background level (2X mean + 3Xstandard deviation).

C3) Citokines multiplex assay. Cryopreserved plasma samples will be used in a 45-plex assay of soluble mediators. The plates will be read with a Luminex instrument (Luminex 200, Austin Luminex, USA) and data will be analysed using MILLIPLEX Analyst 5.1 software (Merck Millipore Darmstadt, Germany). Measures will be performed in duplicates.

C4) Combinatorial flow-cytometry of lineage, activation inducible markers and intracellular cytokines Cryopreserved PBMCs will be stimulated with reactive peptide pools identified by ELISpot and incubated overnight. In the ICS, we will combine T-cell lineage markers (CD3, CD4, CD8, CD45, CCR7, CD27), activation inducible markers (AIMs: OX40, CD25 and CD137) and cytokines (IL2, IFNg, TNF). Samples will be acquired on an LSR Fortessa cytometer (BD), data analysed using FlowJo software v10 and polyfunctional cytokine profiling represented using SPICE v6 (NIAID, NIH).

#### 6.6.2. OUTCOME MEASURES

Outcome measures of immune response (SARS-CoV-2 Antibodies (N), cytokines, T-cells) and Covid-19 clinical symptoms will be measured at baseline and prospectively aiming to observe possible associations between possible prognostic factors and immune response. The baseline and prospective measurements will allow to assess their prognostic role and whether some of them appear as confounding factors.

**Primary Outcome Measure:**

1. Creation prospective cohort of health care workers

Include 675 exposed HCW participants and 675 infected HCW participants against SARS-CoV-2, cohorts will be compared at each time point in terms of sociodemographic, epidemiological, clinical, and immunological information available. an exploratory bivariate analysis will be performed using the tests of Chi Square, ANOVA, Kruskall-Walis, depending on the application conditions assumptions.

[Time Frame: Baseline, to 12 months after the beginning of the study]

2. Cohort description demografics ( age, sex, academic level, housing characteristics, work variables )

Descriptive analysis of the participants will be performed using the number and percentage for categorical variables, and mean and standard deviation or median and quartiles 1 and 3 for quantitative variables, an exploratory bivariate analysis will be performed using the tests of Chi Square, ANOVA, Kruskall-Walis, depending on the application conditions assumptions.

[Time Frame: Baseline, to 12 months after the beginning of the study]

2. Cohort description clinical spectrum (asymptomatic, mild-moderate illness, severe-critical)

Cohort comparison, an exploratory bivariate analysis will be performed using the tests of Chi Square, ANOVA, Kruskall-Walis, depending on the application conditions assumptions.

[Time Frame: Baseline, to 12 months after the beginning of the study]

